**SmartHMD for improved mobility**

**NCT # 03781583**

**IRB approval date 5/29/2021**

## SmartHMD for improved mobility

### PROTOCOL

#### I. BACKGROUND

In 2015, 1.02 million individuals were blind and 3.22 million were visually impaired in the US, with this prevalence expected to double by 2050.(Varma 2016) The economic cost of chronic care for individuals with vision impairment is significant, expected to increase from \$145 billion to \$375 billion during this period ([www.rpbusa.org](http://www.rpbusa.org)). Many patients with blindness or vision impairment are considered as low vision (LV), which is defined functionally as chronic uncorrectable vision loss that impacts daily living or clinically by visual acuity and visual field (VF) criteria ([www.who.int/blindness](http://www.who.int/blindness)).

Numerous studies show that reduced orientation and mobility (O&M) results in the loss of independence, increased depression, and an overall reduced quality of life (Salive 1994; Owsley 2004; Montarzino 2007; Paz 2001). LV limits mobility, and therefore, the independence and health of afflicted individuals. Studies have shown that people with peripheral VF loss are especially impacted by impaired O&M (Geruschat 1998; Haymes 1996). The role of peripheral vision in detecting and avoiding nearby obstacles is a possible explanation for why people with peripheral vision loss experience greater O&M deficits than people with central vision loss (Kuyk 1996)

The prevalence of LV due to peripheral vision loss is not fully known, but one study showed that 21% of individuals with LV had a diagnosis of glaucoma or early-onset retinal degeneration, which commonly lead to peripheral vision loss (Owsley 2009). Another study showed that 14% of patients with LV had one of these diagnoses and stated the possible under-sampling of patients with peripheral VF loss (Goldstein 2012; Brown 2014). These studies underestimate the burden of peripheral VF loss since conditions such as non-glaucomatous optic neuropathies or a history of panretinal photocoagulation treatment for retinal ischemia may cause peripheral field loss, but do so less consistently or were not sufficiently captured in past studies.

Up to 85% of patients with LV may improve their vision-dependent function through low vision rehabilitation. Despite potential benefits of rehabilitation, there has been limited research and few assistive devices for LV due to peripheral vision loss. These devices do not address functional impairments, such as reduced O&M, from peripheral vision loss. Head-mounted display (HMD) technology has potential to benefit individuals with severe peripheral vision loss (Ehrlich 2016). Our team has developed a prototype smartHMD system that functions as a personalized navigation system to enhance vision-dependent functions, in particular O&M, for patients with LV.

#### II. OBJECTIVES/ HYPOTHESIS

Our objective is to assess the impact of smartHMD in several navigation scenarios that people with low vision find difficult to complete. We expect the smartHMD to increase the completion time for navigation task, vs. baseline mobility.

#### III. STUDY DESIGN

##### a. Patient Recruitment

Participants will be enrolled at the Kellogg Eye Center (KEC) and participants will be recruited via mailings or will be identified by a vision care provider. Patients recruited via mailings will be given two weeks to opt-out of the study prior to receiving a phone call. To evaluate eligibility and clinical status, medical records of patients with conditions or treatments likely to result in PFL (glaucoma, retinal dystrophy including Argus 2 implants, optic neuropathy, pan-retinal photocoagulation) will be reviewed. Inclusion and exclusion criteria are summarized in Table 1. Participants will be reimbursed \$100 for their time.

Table 1. Summary of inclusion and exclusion study criteria for participants

INCLUSION CRITERIA	EXCLUSION CRITERIA

 
• Diagnosis of low vision
 
• Self-reported difficulty with mobility and finding doors (either indoors or outdoors) and using signalized crosswalks.
 
• Either sex
 
• Any self-declared ethnoracial category
 
• ≥ 14 years' old
 
• Ability to cooperate for tests
 
• Able to participate in all visits
 
	
 
• Unable to use head mounted display
 
• Unstable age-related macular degeneration within the past 3 months
 
• Unstable diabetic retinopathy within the past 3 months
 
• Unstable diabetes within the past 3 months
 
• Ocular infection or ocular inflammation in the past 3 months
 
• Ocular trauma within the past 6 months
 
• Intraocular surgery within 6 months
 
• Optical coherence tomography retinal findings of concern to investigator for unstable vision during the study
 
• Women who are pregnant (due to risk of falls and change in gait). The study team will ask if a potential subject is pregnant and those who self-report will be excluded.
 
• Uncontrolled seizure disorder in the past 6 months
 
• Cerebrovascular accident occurring in the past 6 months
 
• Parkinson disease or neurological condition that limits mobility
 
• Alzheimer disease or other forms of dementia
 
• Score of less than 18 on MoCA-Blind test
 
• Conditions of concern to investigator that would confound orientation and mobility, such as severe arthritis, pain that limits ambulatory activities, or orthopedic surgery (e.g., hand, arm, shoulder, knee, or hip surgery within 12 months)
 

### b. Experimental Methods and Design

SmartHMD (described in section d) will be evaluated in participants (n=30) with severe VF constriction. The study visit should take up to three hours depending on which experiments are performed. Typically, we will focus on one or two of the five tests described below. For all experiments, the participant's baseline mobility skills will serve as the control. We will first train the participant to ensure they can effectively use the smartHMD. Prior to each task, we will describe the task to them. If the participant does not think they can perform the task with their baseline mobility, they will not be forced to do so. For some experiments, we will blindfold the participants, to remove the variable of residual vision. This has been done in other studies of blind mobility (Rizzo 2018).

#### 1. Outdoor testing: crosswalk detection

We will use crosswalks with signals near the North Campus Research Center. These crosswalks are highly used by pedestrians, thus they have well-maintained signals, crosswalk striping, and pavement. Testing will be done in with verbal, vibrational, and (for Argus II participants) modified video.

Subjects will stand 2 meters from and with their backs facing the intersection. Subjects will then be instructed to walk the intersection. They will then have to align themselves with the crosswalk and point to the pedestrian signal upon locating it. Upon locating the pedestrian signal, subjects will either cross or not cross the street based on their interpretation of the pedestrian signal display (without smartHMD) or by following the cues from the smartHMD (smartHMD).. After an orientation period with the smartHMD (which will include practice mobility trials), subjects will repeat the crosswalk navigation task using smartHMD and, if possible, without smartHMD.

Approximately 12 crosswalk navigation trials will be collected for each condition. To reduce the effects of familiarity with the intersection with repeated visits and trials, four different signalized intersections will be

used and subjects will negotiate each intersection in the forward and reverse direction. The order of walking direction and which signalized intersection will be used will be counter-balanced across subjects and condition. The order of testing with the Baseline or Sham condition first will also be counter-balanced across subjects and signalized intersections.

## 2. Outdoor navigation

The participant will start at a location approximately 50 m or less from a building entry point. The smartHMD will guide the user towards an entry door. The participants starting location will vary. We will conduct 10 trials for each participant.

## 3. Hallway navigation

The participant will be guided by the smartHMD from one location in NCRC to another location. The route will be on the same floor (no stairs or elevators), but may include ramps. A participant may complete up to 10 routes, each about 50 m, with 2-3 turns. The order of routes and smartHMD configurations will be varied across participants.

## 4. Indoor testing: Door detection

Subjects' will use smartHMD technology guided computer vision to navigate toward a door sign located approximately 3 to 4 meters away. This testing will be done in a conference room. The participant's starting point will be at different orientations from the door. The subjects will be stopped to ensure that they are not hit by door opening. We will conduct 8 trials, each with a unique combination of starting point and orientation with respect to the door.

Three experimenters will be present during all navigation trials that are done in common areas, including the outdoor spaces, crosswalks, and hallways. Two will act as a safety officers and flank the subject at all times and the other experimenter will record the navigation outcome measures (defined below). For testing done in closed space, such as a conference room, one safety officer will walk with the participant and one experimenter will record data. After every trial for the experiments listed above, the participant will be offered a seated break.

Prior to the navigation trials, each subject's preferred walking speed (PWS) will be determined by timing how long it takes the subject to walk at their normal pace, along a ~20 meter straight, unobstructed, sidewalk or hallway. Subjects will wear their habitual spectacle correction, if normally worn for mobility activities and no assistive mobility devices (including the smartHMD) will be used when measuring subjects' PWS. Subjects' PWS will be measured four times but only the last three PWS trials will be averaged to represent each subject's PWS due to familiarity effects between the first and second PWS trial.

The smartHMD will include automatic data logging to record video and user command and cue, all time-stamped for later analysis.

For all experiments, time to the complete the route is the primary outcome measure. In contrast to reaction time in speed-critical tasks, time to completion is used here as a continuous measure of task difficulty that encompasses wrong responses and resulting error correction, slow walking due to confusion, and overall efficacy of travel. Our statistical analysis will account for differences in walking speed between participants. Secondary measures include Percentage of Preferred Walking Speed (Patel 2006), # of unintended contacts with obstacles and walls, # of incorrect turns, # of requests for assistance, type of assistance requested, and # of interventions by the experimenter. Data collection will be facilitated by a wearable test system with redundant data collection via hard copy datasheets and a handheld (by an experimenter) video camera. Post-test data processing will refine the measures.

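### At the crosswalk, route completion time does not by definition penalise crossing against the signal, and no listed measure scores the cross-or-wait decision

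*Combined protocol and SAP*

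**What the plan says.** The outcome paragraph of III.b (printed at the end of subsection 4) sets one primary outcome for every test: "For all experiments, time to the complete the route is the primary outcome measure". Its reason is that "time to completion is used here as a continuous measure of task difficulty that encompasses wrong responses and resulting error correction".

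In III.b.1 the participant walks to the intersection, lines up with the crosswalk and must "point to the pedestrian signal upon locating it". After that, "subjects will either cross or not cross the street", going by their own reading of the "pedestrian signal display (without smartHMD) or by following the cues from the smartHMD". The volume is given as follows: "Approximately 12 crosswalk navigation trials will be collected for each condition".

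The secondary measures in III.b are percentage of preferred walking speed, counts "of unintended contacts with obstacles and walls, # of incorrect turns, # of requests for assistance, type of assistance requested", and the number "of interventions by the experimenter". Two safety officers walk beside the participant, a third experimenter records outcomes, and the device logs video, commands and cues with time stamps. Baseline trials are optional: III.b lets a participant decline a task, and III.b.1 asks for trials without the device only where possible. Section III.d uses the results to decide which configuration improves mobility and whether it beats baseline.

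**The concern.** The reason given for using time is sound where an error must be undone. A wrong turn in a hallway has to be walked back, and the clock records it. Crossing on Don't Walk is different: once the participant has reached the far side, there is nothing to correct. The error that this test adds to the other navigation tasks, and the one with the gravest possible harm, therefore has no built-in cost in the primary outcome.

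The conclusion in III.d could then go wrong in two ways. A configuration that cues crossing too early could look as good as a correct one, or better. A configuration that rightly holds back people who would have crossed against the signal at baseline could look no better than baseline, or slower.

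I take shorter time as better, which follows from calling time a measure of difficulty. Section II expects the device to lengthen completion time, which points the other way. If longer were better, unnecessary waiting would be rewarded, and time would still not measure correctness.

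**Working it through.** **1. What each clock rule does.** The plan does not say when the clock stops if the participant waits.

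| Clock rule | Unstopped wrong crossing, against a correct wait |
|---|---|
| Runs through the wait to the far kerb | Faster, by the wait that is skipped |
| Stops at the decision | Same |
| Pauses during the signal wait | Same |

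A fourth rule, timing only trials that end in a crossing, would time wrong crossings and leave correct waits without a value. It is an unlikely intention. Under the assumed timings in step 3, an always-correct device would have no time in 12 x (C - W)/C = 10, 9.3, 9 or 11 of its 12 trials.

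**2. What the secondary measures do.** Walking speed is speed-based, as time is. Contacts, turns and requests for assistance do not refer to the signal. Interventions may include an officer stopping a step-off, but the count also takes in other help and does not record the signal state. It cannot separate a correct wait from a wrong one.

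**3. Illustrative size if the clock includes the wait.** The plan has no figure for this, so every input here is assumed. Cycle length is C and Walk interval W, and the ready-to-cross moment falls uniformly over the cycle. The gap g is the difference between conditions in wrong crossings, as a share of Don't Walk arrivals. A share s of wrong crossings is stopped, and a stopped trial takes about as long as a correct wait.

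- Mean wait skipped by one unstopped wrong crossing: (C - W)/2.
- Mean correct wait per trial: [(C - W)/C] x (C - W)/2 = (C - W)²/(2C).
- Shift in mean time towards the less safe condition: g x (1 - s) x (C - W)²/(2C).

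| C/W (s) | Wait skipped (s) | Mean correct wait (s) | Shift, g = 0.20, s = 0 | s = 0.5 | s = 0.9 |
|---|---|---|---|---|---|
| 60/10 | 25 | 20.8 | 4.2 | 2.1 | 0.4 |
| 90/20 | 35 | 27.2 | 5.4 | 2.7 | 0.5 |
| 120/30 | 45 | 33.75 | 6.8 | 3.4 | 0.7 |
| 120/10 | 55 | 50.4 | 10.1 | 5.0 | 1.0 |

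With g = 0.05 and s = 0 the shifts are 1.0, 1.4, 1.7 and 2.5 s. The opposite, safe error does cost time: a wrong wait on Walk adds C - W/2 on average, which is 55, 80, 105 or 115 s.

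**4. Scale.** The plan's SD is 33% of the mean, from 13/41 (31.7% by arithmetic). At 90/20 s with an assumed 45 s for the rest of the trial, the mean is 45 + 27.2 = 72.2 s. The 20-point shift is then 5.44/72.2 = 7.5% of the mean with no stops, and 2.72/72.2 = 3.8% with half stopped.

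**5. Can the ranking reverse?** Take C = 90 and W = 15, so the mean correct wait is 75²/180 = 31.25 s. Suppose an always-correct device cuts the other route time from 60 to 48 s. Its mean is 48 + 31.25 = 79.25 s.

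- Baseline with 50% unstopped wrong crossings: 60 + 0.5 x 31.25 = 75.6 s. The better device looks slower.
- Baseline with 25%: 60 + 0.75 x 31.25 = 83.4 s. The device looks faster. A 50% error rate with half stopped gives the same figure.

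Reversal is possible but depends on the inputs.

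**The case against.** The strongest reply has four parts.

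- **A wrong crossing gains time only under one clock rule.** This stands. Under the other plausible rules time is neutral. Neutral still means that the outcome cannot tell a right decision from a wrong one.
- **Officers are beside the participant.** A stopped step-off may be counted as an intervention, and the return to the kerb may add time. This stands too: the bias shrinks towards zero as more wrong crossings are stopped, and a stopped error may be mildly penalised. The plan does not say when officers must stop a crossing, so the share is unknown.
- **The data already exist.** The video and cue log would allow decisions to be scored, the secondary list may not be exhaustive, and the plan foresees refining measures after testing. This is correct, so the gap is one of pre-specification. No decision measure is defined from those records.
- **The study is small and largely descriptive.** Section III.d does stress listings and summaries. It also intends to say which configuration improves mobility and whether it is significantly better than baseline, and that claim needs an outcome that sees the decision.

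A reader might infer that the trial will favour an unsafe device, or might simulate how often such a device would test significantly faster. The documents do not support either. The plan names no test for completion time, and the signal timing, error gap, stop rate, correlation and number of participants in this test would all have to be assumed.

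**Conclusion.** The point holds in a limited form, and the plan should be changed. For the crosswalk test, route completion time does not by definition penalise crossing against the signal, and no listed measure compares the decision with the signal. Time alone therefore cannot support a conclusion that a configuration improves crosswalk mobility. This part rests on the text and needs no assumed number.

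The size of any bias is unknown. The range in the working, from 10.1 s per trial with no stops down to 0.4 s with 90% stopped at a 20-point gap, depends wholly on assumed inputs and on a clock that runs through the wait.

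Three stronger readings go too far. Crossing errors are not lost to the study, because the recordings can show them. Decision correctness need not be co-primary: a named key outcome reported beside time closes the gap. Nor does the defect call for a rule suspending device trials; that is a separate question of participant safety, and flanking officers are already planned.

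**What to change.** In III.b.1:

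- (a) In each crosswalk trial, record the displayed signal at the decision, the device cue, the decision, and any officer stop. Confirm these from the video and log.
- (b) Add the share of correct decisions per participant and condition as a named key outcome reported beside time. Correct means crossing on Walk and waiting on Don't Walk; an officer-stopped step-off on Don't Walk counts as wrong. List every wrong crossing.
- (c) Exclude the signal wait from crosswalk completion time, and state how trials that end in waiting or in an officer stop are timed. Time to pointing at the signal may be reported as an optional component, since it precedes the decision and contains no wait.
- (d) Do not call a configuration an improvement at crosswalks on time alone. Report wrong crossings for every device configuration. Give the device-minus-baseline difference, with a confidence interval, only in participants who did both conditions, and state how many declined baseline.

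The cost is one paragraph and four datasheet fields per trial, using staff, video and logs already planned. The main drawback is imprecision if errors are few. With an assumed 10 participants x 12 trials treated as independent, 0 errors in 120 still allows a rate of up to 1 - 0.05^(1/120) = 2.5% (one-sided 95%).

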## c. Subject Interviews and Surveys

We will administer standard and custom surveys to the participant to obtain more information about their condition, difficulties they face due to visual impairment, and preference for the smartHMD design. A copy of all 5 surveys are attached in the Additional Supporting Documents section. The interviews will be recorded.

MoCA-Blind (Montreal Cognitive Assessment) is an adapted version of the original MoCA ([www.mocatest.org](http://www.mocatest.org)), a rapid screening instrument for mild cognitive impairment. We will use the recommended cutoff value of  $\geq 18$  to screen participants for suspected cognitive impairment or dementia. Data will be scored using the recommended summary scoring algorithm that includes scores on items corresponding to memory, attention, sentence repetition, verbal fluency, abstraction, and delayed recall and orientation. We will conduct this survey on the pre-screening phone call.

IVI-VLV (Impact of Visual Impairment – Very Low Vision) is a standard survey to assess vision-related quality of life in persons with severe vision loss (Finger 2014). This survey will be administered prior to testing and may be administered over the phone as part of the pre-screening phone call.

SmartHMD in-test questions. We will ask the participants to rate their trust in the system and to rate the mental energy required to use the system.

SmartHMD post-test questions. After testing, we will ask the user follow up questions to obtain their impressions from testing.

SmartHMD follow up phone call. We will contact the participant 1-2 weeks after testing to ask them a series of follow up questions, since they may have more thoughts on the system design.

#### **d. Data Analysis**

Data analysis will be done to determine which configuration of the smartHMD device improves O&M in study participants who have LV, and if improvements are significantly better than baseline mobility.

The peer-reviewed literature provides estimates of mean PPWS and variability within groups of LV subjects. PPWS can be viewed as a surrogate measure for completion time, and its reported variability among LV subjects is useful for sample size estimation. Other groups (Soong, 2004) have reported on two visually impaired groups ( $n=19$  &  $n=18$ ); the mean (SD) PPWS values for the two groups were 40.1% (12.7%) and 40.8% (13.1%). Thus, we estimate the SD to be 33% ( $\sim 13/41$ ) of the mean completion times for both baseline and smartHMD conditions. Our prior work (Adebiyi 2017) compared guided mobility (with verbal or vibrational feedback) versus no guidance and found significant differences in completion time with  $n=11$  participants. Thus our subject pool of 30 should be adequate to yield rigorous results.

Given the small sample size, an informative way to present the data will be through listings of the raw data. Listings will show subject disposition, demographic and baseline characteristics, extent of exposure and study termination/withdrawal information, as well as efficacy information. Descriptive statistics (number and percentage for categorical data; mean, median, standard deviation, inter-quartile range, min/max, and number for continuous data) will be presented for each evaluable for differences in outcomes control vs. smartHMD condition. For discrete variables, descriptive analyses will be based on numbers of subjects and related percentages.

Interviews will be audio-recorded, transcribed verbatim, and analyzed using inductive qualitative analysis. Additionally, mixed methods analyses, such as joint display tables, will be used to integrate qualitative findings with vision-related quality of life data from the IVI-VLV. These analytic approaches will provide insights on how user preferences vary based on vision-related quality of life across various domains.

Data from the IVI-VLV correspond to two domains: Activities of Daily Living, Mobility and Safety and Emotional Wellbeing. Survey response data will be scored using classical approaches (e.g. Likert scoring). Modern psychometric approaches are preferred, however. Thus, if a Rasch-analysis produces stable items calibrations (e.g.  $\pm 1/2$  logit with 95% confidence), IVI-VLV response data will be Rasch-adjusted.

A score of 18 (out of 22) on MoCA-Blind is considered normal. This is not used for statistical analysis but as a screening tool.

All data listings, summaries, figures, and statistical analyses will be generated using SAS Version 9.3 or higher (SAS Institute, Cary, NC), R (R Foundation for Statistical Computing, Vienna, Austria), or other validated statistical software.

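### The plan asks whether smartHMD is significantly better than baseline, but states no test, interval, unit of analysis or walking-speed step for completion time

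*Combined protocol and SAP*

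**What the plan says.** Completion time is primary throughout: "For all experiments, time to the complete the route is the primary outcome measure" (Section III.b, outcome paragraph after the door-detection test). The comparison is within person: "For all experiments, the participant's baseline mobility skills will serve as the control" (III.b, opening paragraph).

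Section III.d gives the analysis two aims: to find which smartHMD configuration improves mobility, and to find "if improvements are significantly better than baseline mobility". For the navigation outcomes it then offers two things:

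- Listings: "Given the small sample size, an informative way to present the data will be through listings of the raw data".
- Descriptive statistics, which "will be presented for each evaluable for differences in outcomes control vs. smartHMD condition".

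The rest of III.d covers interviews (qualitative analysis), the IVI-VLV survey (Likert or Rasch scoring) and software.

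Two further statements bear on the point. Trials are repeated; for the crosswalk test, "Approximately 12 crosswalk navigation trials will be collected for each condition". The outdoor, hallway and door tests have 10, up to 10 and 8 trials, with no statement of how these divide between conditions. On walking speed, III.b promises: "Our statistical analysis will account for differences in walking speed between participants". Preferred walking speed (PWS) is measured four times and "only the last three PWS trials will be averaged to represent each subject's PWS". Percentage of preferred walking speed (PPWS) is listed as a secondary measure.

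**The concern.** The aim is inferential, but the analysis stated for the outcome that carries it is descriptive. A mean and SD of differences may suggest a benefit. They do not supply the significance statement that III.d says it seeks, and no alpha, sidedness, test, model or interval for completion time appears anywhere.

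Two gaps make this more than a missing detail. First, trials from one person are correlated, and nothing says how they are combined. The analyst can treat them as independent, pair them or average them, and the error rate depends on which. Second, the promise on walking speed has no step that carries it out for the primary outcome.

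At stake is whether any later claim of benefit rests on a method fixed in advance or on one chosen once the data are visible.

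**Working it through.** **The plan's own figures.** The SD input is close to its source: 12.7/40.1 = 31.7%, 13.1/40.8 = 32.1% and 13/41 = 31.7%, rounded up to 33%. The sample size of 30 cannot be reproduced, because III.d gives no alpha, power, effect size or within-person correlation. It therefore does not reveal which test was intended.

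**Unit of analysis.** The documents give no within-person variances, so these are assumptions on the log-time scale: trial SD s = 0.25, participant-by-condition SD τ = 0.10 to 0.20, between-participant SD b = 0.32 (close to the plan's 33%), two-sided alpha 0.05. The 12 trials per condition come from the crosswalk test. Values of 4 to 5 assume that the 8 to 10 trials of the other tests are split evenly between two conditions.

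*Pooled paired trials.* The ICC of the trial differences is τ²/(τ² + 2s²), with 2s² = 0.125:

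- τ = 0.10: 0.01/0.135 = 0.074
- τ = 0.20: 0.04/0.165 = 0.242

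The true standard error exceeds the pooled one by r = √(1 + (m − 1)·ICC), and type I error is about 2·(1 − Φ(1.96/r)).

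| m per condition | τ | r | Type I error |
|---|---|---|---|
| 12 | 0.10 | √1.815 = 1.35 | 14.6% |
| 12 | 0.20 | √3.667 = 1.91 | 30.6% |
| 4 | 0.10 | √1.222 = 1.11 | 7.6% |
| 5 | 0.20 | √1.970 = 1.40 | 16% |

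Simulating the same model agrees to within about a percentage point. If the 8 or 10 trials were instead per condition, the results fall between these rows for the same τ.

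*Pooled unpaired trials.* The true variance of the difference is proportional to τ² + 2s²/m. The variance used is (2b² + 2s² + τ²)/m, with 2b² + 2s² = 0.2048 + 0.125 = 0.3298.

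- m = 12, τ = 0.20: true 0.0504, used 0.3698/12 = 0.0308. The ratio of standard errors is 1.28 and type I error is about 13%.
- m = 4, τ = 0.10: true 0.0413, used 0.3398/4 = 0.0850. The ratio is 0.70 and type I error is below 1%.

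These are large-sample values. Simulation with 6 to 30 participants gives about 1% to 15% over the same range.

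*One mean difference per participant.* A paired t-test on these means gives about 5% throughout.

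**Walking speed.** Over distance D, completion time is T = D/(PWS × PPWS). On a 50 m route (hallway test) at 40% PPWS (the level cited in III.d), with assumed walking speeds and an assumed 20% benefit:

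- 1.2 m/s: 50/0.48 = 104 s, benefit 21 s
- 0.7 m/s: 50/0.28 = 179 s, benefit 36 s

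The ratio is 0.80 for both. If the effect is proportional, a within-person ratio removes walking speed and a difference in seconds does not. Dividing T by D/PWS also normalises it. III.d specifies neither for completion time.

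**The case against.** The strongest reply is that III.d is under-specified, not descriptive by design. It calls listings an informative way to present data, not the only way; III.b refers to a statistical analysis; and the software sentence names statistical analyses separately from listings and summaries. That is fair. A reader might infer that the plan rules out inference, and the text does not go that far. But no method is supplied, so the plan as written still does not answer its question.

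A reader might also infer that the trial will be tested on pooled trials with a badly inflated false-positive rate. The documents do not support this. No section proposes a trial-level test, participants are their own controls, and III.d reasons in numbers of participants. Nor does pooling always inflate error: unpaired pooling can be conservative. Inflation is a risk left open.

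On walking speed, the measurement is planned, PPWS is a speed-normalised secondary measure, and the comparison is within person. All of this stands; only the step for the primary outcome is missing. The advantage of a ratio scale also presumes a proportional effect, which the documents do not establish.

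Finally, it is tempting to argue that analysing in seconds loses material power. A gap of 68–69% versus 80% appears only with an assumed 12 participants and log-ratio SD 0.25. The variances assumed above at 12 trials imply √0.0204 = 0.14 to √0.0504 = 0.22. With 30 participants both scales reach at least 97%. That argument should not be used.

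**Conclusion.** The point holds as a change that should be made. For completion time the plan states no test, no interval and no unit of analysis, and gives no step that carries out its promise on walking speed. That conclusion rests on the text alone.

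The size is conditional. The calculated error rates run from about 1% to about 31%, depending on the form of the test, the trial count and variances that the documents do not give. They show that the open choice is consequential; they do not predict the trial's error rate. The planned data remain usable, and a participant-level analysis holds about 5% under the same assumptions.

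**What to change.** Add a paragraph to III.d along these lines:

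- **Primary analysis, for each test:** compare smartHMD with baseline at participant level. Use a paired t-test on each participant's mean log completion time per condition, or a mixed model on log time with participant intercept and participant-by-condition slope, adding route and order terms where the data support them.
- **Reporting:** the smartHMD/baseline time ratio with 95% CI and two-sided p-value.
- **Walking speed:** state that it is accounted for through within-person log ratios, or through time divided by distance/PWS. The latter is also useful where route lengths differ between conditions.
- **Configuration:** fit it as a factor, so that the first aim of III.d is answered too.
- **Multiplicity:** state how several tests and several configurations are handled.
- **Skipped baseline runs:** III.b allows participants to decline a task at baseline. Report these participants separately; a complete-pairs analysis would silently drop people who may be the least able.

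Keep the listings and descriptive statistics as support. The cost is one paragraph of text and a little more analysis work, with no new data. Intervals may be wider than a pooled-trial analysis would show.
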